GDPR	General Data Protection Regulation
IRAS	Integrated research application system
MS	Multiple Sclerosis
MSIS-29	Multiple Sclerosis Impact Scale (29 items)
MS-WIS	Multiple Sclerosis Work Instability Scale
NFI-MS	Neurological Fatigue Index for Multiple Sclerosis
NHS	National Health Services
PwMS	People with multiple sclerosis
READY(for MS)	Resilience for Adults Everyday
REC	Research and ethics committee
R&D	Research and development
SUS	System useability scale
USE-MS	Uni-dimensional Self-efficacy Scale for Multiple Sclerosis

STUDY SUMMARY

Study Title	Preventing job loss using Acceptance and Commitment Therapy in Vocational Rehabilitation
Internal ref. no. (or short title)	MS-PROACTIVE
Study Design	Randomised external pilot trial
Study Participants	Patients with multiple sclerosis
Planned Size of Sample (if applicable)	92
Follow up duration (if applicable)	6 months
Planned Study Period	24 months
Research Question/Aim(s)	
1. To adapt the READY for MS Acceptance and Commitment Therapy programme to a digital format for use in the UK.2. To assess the efficacy of using web-based ACT versus standard care in a randomised pilot study

FUNDING AND SUPPORT IN KIND

FUNDER(S) (Names and contact details of ALL organisations providing funding and/or support in kind for this study)	FINANCIAL AND NON FINANCIAL SUPPORT GIVEN
MS Society MS National Centre [name]	Total: £149,950.25 Salaries: £111,480.25 Non-salaries: £38,470.00
Leeds Teaching Hospitals NHS Trust [name] University College London	Study site, provision of premises for study participant visits and assessments Study site, provision of premises for study participant visits and assessments

ROLE OF STUDY SPONSOR AND FUNDER

- Develop strategies to encourage recruitment and address any issues with recruitment
- Be involved in the day-to-day running of the study by supporting the Chief Investigator
- Provide clinical or other expert guidance on clinical and practical queries and interpretation of data collected
- Provide responses to any issues or concerns raised by the chief investigator or the external ethics committees
- Input into the development of the statistical analysis plan
- Input into the interpretation and writing up of the study results

- Presentation of the study results at scientific meetings and in written publications

Schedule of meetings of the trial management group

The TMG will meet formally on a quarterly basis during the course of the study to monitor progress, completion of appropriate assessment and troubleshoot any issues raised during the study, either by participants or other members of the TMG. The agenda of these meetings and timetable will be driven by the chief investigator. It is anticipated the chief investigator will meet with individual members of the TMG more frequently as required. The patient representative will not be needed to attend all the TMG meetings, but will be invited to meet with the TMG on a six monthly basis to provide input on the progress of the study and future direction. The TMG meetings will be minuted and a record kept in the study file.

We will convene a Trial Steering Committee (TSC) who will meet formally in Year 1 and Year 2 of the study. Any significant concerns from the Trial Management Group will be escalated to the TSC. The TSC will receive the minutes from the TMG and a formal report of the progress of the study.

PROTOCOL CONTRIBUTORS

The protocol for the study has been developed by the chief investigator and co-investigators with advice from lay reviewers and the MS Society Grant Review Panel. The initial proposed study plan was submitted to the MS Society Research Network for advice on the application development. We received detailed reviews from five lay reviewers on developing the project plan. Based on the reviews we developed the proposal by adjusting the time frame of questionnaires, providing more detail on the content and length of on-line sessions, included MS nurse support and provided further information about previous testing of READY for MS in Australia and Italy. The revised proposal was then submitted to the MS Society Grant Round. The project received external peer and lay reviews. The final protocol has included advice and recommendations from the Grant Review Panel prior to confirmation of MS Society funding.

PLAIN ENGLISH SUMMARY

Up to 80% of people with MS (PwMS) leave employment within ten years of MS onset. Complex personal and workplace factors influence job loss. Self-efficacy has been highlighted as a key factor in job retention for PwMS.

An Acceptance and Commitment therapy (ACT) course called 'READY for MS' has been developed in Australia. ACT has been shown to improve self-efficacy. This trial aims to adapt and measure the feasibility of using an online version of this course in the NHS.

Researchers will work with a digital company and the developer of READY for MS to develop an online version. This will then be tested by four people with MS. Based on their detailed feedback the online version will be adapted. We will then recruit and randomise 88 PwMS in Leeds and London who are at potential risk of job loss. Participants in the active treatment group will use the online treatment and standard care from their local MS teams; the control group will receive standard care.

[figure not shown]
Participants will be asked to complete questionnaires at the start of the study (baseline), 8 weeks and 6 months. The questionnaires will measure work, self-efficacy, mood, quality of life, fatigue and the impact of MS. The questionnaire data will be analysed to test the effectiveness of the treatment.

We also want to find out how the use of the online treatment works in practice. This is known as process evaluation and will help with any future use of the online READY for MS sessions. Four PwMS in each centre will be asked to consent to be interviewed before they start doing the course, at 12 weeks and at 6 months. This qualitative interview data will be evaluated to understand the experience of the participants using READY for MS.

This pilot trial may lead to a larger randomised control trial and application to the wider UK population. This cost-effective treatment could help PwMS improve self-efficacy in and beyond employment.

STUDY FLOW CHART

FLOW CHART MS-PROACTIVE Pilot: Preventing job loss using Acceptance and Commitment Therapy in Vocational Rehabilitation (IRAS 279736)

STUDY GANTT CHART

See Appendix

STUDY PROTOCOL

1 BACKGROUND AND RATIONALE

Multiple sclerosis (MS) is the commonest acquired disabling neurological disease affecting young adults. MS affects approximately 120,000 people in the UK and 2.5M globally. The onset of MS is typically, in working age adults between 20 and 40 years of age. It is common for people's working life to be adversely affected with 50%–80% of people with multiple sclerosis (PwMS) losing employment by 10 years after disease onset. The Multiple Sclerosis International Federation Survey on MS and Employment found that almost half of the people leaving the workforce did so within three years of diagnosis (MSIF 2010). 75% of PwMS in a Work Foundation study reported that their condition had impacted their employment and career opportunities (Bevan, Zheltoukova & McGee, 2011). More than half of PwMS who are not in paid employment would ideally like to be in work (Wetherly & McIntosh, 2016).

Most people with MS in the UK are in full-time education or employment at the time of diagnosis. People with MS struggle to continue working and a higher percentage of people with MS are unemployed than in the rest of the population (Sweetland, Howse & Playford, 2012). Estimates of work retention vary in the UK, USA and Europe with between 20 and 30% remaining employed 5-17 years after diagnosis. The unpredictable nature of MS causes problems for people with MS and their employers. Many MS symptoms are 'invisible' making it difficult for employers to understand. The employer burden is significant in terms of absenteeism and disability costs. People with MS and their employers are not always sure how to implement effective accommodations, particularly if these relate to mental health (Frndak et al., 2015). Lack of knowledge or timeliness in implementing effective accommodations can create barriers to continued employment (Nevala, Pehkonen, Koskela, Ruusuvoori & Anttila, 2015). Employers are less likely to grant accommodations that involve schedule adjustments or expensive devices (Rumrill, Fraser & Johnson, 2013). The economic impact of loss of employment has huge implications for people with MS, their families and society. Women with MS are more

likely to withdraw from the workforce and this may be linked to taking on additional responsibilities at home.

One of the NHS 5 year forward (2014) aims was to help develop and support new workplace incentives to promote employee health and cut sickness-related unemployment. Sickness absence related costs to employers and taxpayers have been estimated at £22 billion a year. Emerging evidence suggests that well targeted health support can help keep people in work thus improving their wellbeing and preserving their livelihoods. Different factors have been described as predicting which PwMS may develop problems at work, including gender, socio-economic status, age, MS symptoms, psychological and emotional factors, workplace variables and disability benefits. However, the reasons for actual job loss often involve complex interactions between these different variables. The level of reported physical disability does not explain the high rate of unemployment. Self-efficacy and negotiating workplace accommodations have been consistently highlighted as key factors for job retention for PwMS. (Gist & Mitchell, 1992; Wilski & Tasiemski, 2016). PwMS who have higher levels of self-efficacy are less likely to need to reduce their working hours within the first year following diagnosis (Jongen, Wesnes & van Geel, 2014).

Work instability (WI) precedes job loss and describes the extent of any mismatch between functional (in) capacity and work demands at a point in time. When WI is present the individual is vulnerable to job loss, and this is the time at which vocational rehabilitation is of greatest preventive importance. A measure of work instability was first developed in rheumatoid arthritis and a robust MS-specific scale, the Multiple Sclerosis Work Instability Scale (MS-WIS) has been generated with PwMS (McFadden et al., 2012). The MS-WIS provides clinical teams the means to screen PwMS to facilitate early, appropriate referral for vocational rehabilitation intervention (evidence for VR). In our study of employed PwMS, high baseline risk on the MS-WIS and low levels of self-efficacy were the key variables associated with actual job loss ([name], Wicks, Stroud & Tennant, 2019).

There is a need for early intervention for employed PwMS to prevent job loss. Improved self-management has been linked to maintained employment (Bishop, Frain, Rumrill & Rymond, 2009). Developing skills in self-

efficacy can enable PwMS to cope with discrimination, to solve problems systematically, request accommodations, negotiate solutions and effectively communicate in the work place (Roessler & Rumrill, 1994). Self-efficacy was identified as being the missing link between MS and employment (Rumrill, 2009).

Acceptance and commitment therapy (ACT) offers a meaningful early intervention in this context. A 'third-wave' cognitive behavioural therapy, ACT utilises empirically supported therapeutic processes including a combination of acceptance, mindfulness, values and traditional behaviour change techniques. These processes cultivate psychological flexibility, the cornerstone of mental and physical health and resilience, and reduce experiential avoidance, a core pathological process whereby behaviours are rigidly guided by thoughts, feelings, and other psychological experiences, rather than one's values (that which would be meaningful) or direct contingencies (that which would be effective). Six interrelated and interdependent processes are identified as contributing to psychological flexibility: [1] acceptance (willingly allowing all experiences to take place), [2] cognitive defusion (the ability to distance oneself from cognitions), [3] contact with the present (non-judgemental awareness of the present moment), [4] values (defining what is important to an individual), [5] committed action (acting in accordance with those values), and [6] self-as-context (flexible perspective-taking) (Hayes, Luoma, Bond, Masuda, & Lillis, 2006). According to the ACT model, an individual's attempts to eliminate or resist unpleasant internal experiences e.g. thoughts, emotions and sensations, can paradoxically increase distress and inhibit the ability to lead a meaningful life (McCracken, 1998). ACT interventions seek to encourage more flexible responses that enable a richer life (Hayes, Strosahl, & Wilson, 2012).

By reducing psychological inflexibility, ACT can treat a very broad range of psychological problems. Accordingly, more than 100 randomized controlled trials (RCTs) (Hooper & Larsson, 2015) have found ACT to be effective and, in turn, it is considered a trans-diagnostic model, appropriate to addressing the challenges encountered in a range of conditions, including chronic illnesses, and contexts, including the workplace. Given the myriad of difficulties that PwMS may face at work, the generic trans-diagnostic nature of the ACT processes are particularly helpful.

ACT interventions can improve physical wellbeing and quality of life and reduce anxiety and depression in PwMS (Hill et al., 2017; Nordin & Rorsman, 2012; Sheppard, Forsyth, Hickling & Bianchi, 2010). ACT has also been shown to be effective in addressing the particular challenges of (non-disabled) employees in the workplace (Burton, [name] & Brown, 2010; Lloyd, Bond & Flaxman, 2017; Hayes, Strosahl & Wilson, 2012). ACT has been shown to improve self-efficacy and resilience in both chronic conditions (Khashouei, Ghorbani & Tabatabaei, 2017; Lappalainen et al., 2014) and the workplace (Burton, [name] & Brown, 2010) indicating a key opportunity to apply ACT for purposes of vocational rehabilitation. However, capitalising on the potential applications of ACT in this context - at the intersection of health and work, and to prevent job loss in PwMS - has been under-utilised. We address this gap through development and adaptation of an online ACT intervention.

REsilience for Adults EverydaY (READY) is an ACT training programme developed in Australia which has been tailored to specific contexts (Burton, [name] & Brown, 2010). READY has been shown to improve resilience, role functioning and quality of life (QoL) in a non-clinical workplace sample and in people with a range of chronic illnesses including MS (Burton et al., 2010; [name], Mawdsley, Brown & Burton, 2018) The READY programme tailored for MS demonstrated improvement in resilience, quality of life, depression, stress, and protective factors in PwMS ([name] et al., 2018). A RCT of the READY programme for MS showed that the participants receiving READY reported significantly better mental health, QoL and less distress compared to relaxation therapy participants (Giovannetti et al., 2019). ACT self-management programs are often conducted in group settings (Hill et al., 2017). However, this presents challenges in terms of access equity and immediacy of support. Remote interventions are increasingly being suggested as an effective, non-threatening, and less resource intensive method for vocational rehabilitation for PwMS (Dorstyn et al., 2017). A series of RCTs has evaluated the efficacy of ACT in web-based self-help formats with positive outcomes in patients with depression and chronic pain (Lappalainen et al., 2014) (Trompetter, Bohlmeijer, Veehof & Schreurs, 2015). Viskovich & [name] (2018) have developed and evaluated a digital READY ACT programme for promoting

mental health in students called YOLO. The digital READY for MS Programme is based on the READY for MS group programme. It will adapt some elements of the YOLO web-based ACT programme. The research team will assess the feasibility of this programme to address the specific challenges of MS and the workplace in the UK.

Effective job retention interventions need to be flexible and easily accessible for employed people. Our PwMS advisors favour an intervention to improve self-efficacy that is convenient (i.e. does not require additional leave from work, ideally web-based, brief and flexible) and empowers them to take control and manage their own situation. They favoured signposting from their MS clinical team where their MS condition is managed and where there is greater understanding and familiarity with access to support networks rather than their GPs. Use of the digital READY ACT intervention would increase fidelity, enable wide and rapid dissemination and could be supported by the wider clinical team (e.g. telephone support by MS nurses) providing a likely practical and cost-effective method for addressing barriers to engagement such as lack of time, immobility, inconvenience or perceived stigma. PwMS have consistently reported they wanted to be more informed and involved with their own care and one of the MS Society's Top 10 priorities is 'How can people with MS be best supported to self- manage their condition?' This research is important because there is a potentially effective and cost-effective intervention for PwMS which can be adapted and tested for use in the UK.

2 RESEARCH QUESTION/AIM(S)

There is a type of treatment which improves self-efficacy and resilience called 'Acceptance and Commitment Therapy'. A type of ACT has been developed in Australia specifically for PwMS called 'READY for MS'.

Our aims are:

- To develop a new digital online version of READY for MS that can be used on a computer without PwMS having to go to hospital or a clinic to see a psychologist.
- To test whether this works in a small pilot study with PwMS in the NHS.
- In the longer term we want to see whether READY for MS can help PwMS stay in work.

2.1 Objectives

- To develop and adapt the READY for MS web-based Acceptance and Commitment Therapy programme for use in the UK.
- To assess the efficacy of using web-based ACT versus standard care in a randomised study.
- To use MS-PROACTIVE to provide the key underpinning data to support the delivery of a definite trial externally funded via the NIHR HTA programme.

2.2 Outcomes

- Primary Outcome: MS Work Instability Scale (MS WIS) at 6 months after randomisation: 22-item, self-administered scale measuring work instability.
- Secondary outcomes: Health related quality of Life (EQ-5D, SF-12), mood (HADS), self-efficacy (Uni-dimensional Self-efficacy Scale for Multiple Sclerosis - USE-MS), impact of MS (Multiple Sclerosis Impact Scale-29, MSIS-29), fatigue (Neurological Fatigue Index for multiple sclerosis - NFI-MS), psychological flexibility (Comprehensive assessment of Acceptance and Commitment Therapy processes -

CompPACT), participant satisfaction with the technology post-intervention (system usability scale - SUS).

3 STUDY DESIGN and METHODS of DATA COLLECTION AND DATA ANALYSIS

DESIGN: This is an external pilot trial. The main purpose is to assess the efficacy of the new online version of READY for MS. The process evaluation will assess the methods of recruitment, randomisation and follow up for a future full trial. The trial is a two centre, two-arm individual patient randomised control trial. We plan to recruit people with a confirmed diagnosis of MS in paid employment attending regional outpatient MS clinics in Leeds and London. The planned follow up is 6 months post-intervention.

SETTING: Recruitment from outpatient MS clinics in 2 regional NHS MS centres. The intervention will be self-managed flexibly in the home setting.

CENTRES: Leeds Teaching Hospitals NHS Trust (CI HF) and Queen Square MS centre, University College London (Co-I WB).

TRAINING: We will hold a training workshop on 'READY for MS' in Leeds for the investigators and the MS Specialist Nurses from the two recruiting centres.

RANDOMISATION: 1:1 by patient. Randomisation will be managed by an independent statistician.

INTERVENTION: The intervention to be tested is the digital version of the READY for MS group programme ([name] et al., 2018) adapted for the UK setting. This will be used with standard care with a written information leaflet about employment and MS 'Work and MS: An employee's guide' (MS Society, 2015).

The group version of READY for MS has been successfully implemented with Australian and Italian PwMS. Implementation in Italy only required minor language adjustments in the translation of content into Italian, but otherwise no other changes were necessary ([name], personal communication). The digital version of the READY for MS Program will consist of 7 weekly modules and a booster session module delivered five weeks after the 7th module. The 7 modules are as follows: Introduction to the READY Resilience Model, Mindfulness, Defusion, Self-as-context, Acceptance, Values and Meaningful Action, and Review and Future Planning. Each

module will be of approximately 30 minutes duration. The modules will consist of engaging animated presentations, guided experiential exercises, video clips, audio files and written exercises. The digital program will be accompanied by a digital copy of the READY Participant Workbook which consists of two parts: written content for each module and the READY Personal Plan. The READY Personal Plan is an important resource as it contains reflection exercises and directed home practice tasks that are undertaken during and between modules.

The adaptation phase will comprise an iterative process of user testing and content development to tailor 'READY for MS' to a UK workplace context. This will involve drawing on relevant principles of experience based co-design (Chisholm, Holtum & Springham, 2018) and digital user experience (UX) testing methodologies to assess user 'journeys' and relevance for self-guided therapeutic application in a range of UK workplace settings. READY for MS will be initially reviewed by the project team for its alignment with research objectives and outcomes, and any immediate changes made. 4 people PwMS (representative of genders, ages and educational level) will then be recruited to experientially review the digital program in terms of its suitability for a UK workplace context. The feedback of 2 employers will also be sought to enhance the co-design process. Participants' feedback will be considered by the research team and program modifications implemented accordingly for a final round of review. In particular, we will consider how the workbook, reflection exercises and directed home practice tasks can be tailored further to represent challenges typical to PwMS in UK workplaces. This process of user testing will also allow consideration of the form and nature of support provided by MS Specialist nurses to support therapeutic engagement.

There is a risk of a high rate of attrition with on-line psychological treatment. The MS Nurses will receive training in the READY programme and will provide planned telephone support at 2-3 weeks post-randomisation. Adherence and completion of the programme will be measured.

CONTROL: Standard care with a written information leaflet about employment and MS 'Work and MS:

IRAS 279736

An employee's guide' (MS Society, 2015).

PRIMARY OUTCOMES: MS Work Instability Scale (MS WIS) at 6 months after randomisation: 22-item, self-administered scale measuring work instability.

SECONDARY OUTCOMES: Health related quality of Life (EQ-5D, SF-12), mood (PHQ9), self-efficacy (Uni-dimensional Self efficacy Scale for Multiple Sclerosis - USE-MS), impact of MS, (Multiple Sclerosis Impact Scale-29, MSIS-29), fatigue (Neurological Fatigue Index for multiple sclerosis - NFI-MS), psychological flexibility (Comprehensive assessment of Acceptance and Commitment Therapy processes - CompPACT), participant satisfaction with the technology post-intervention (system usability scale - SUS).

PROCESS EVALUATION

The process evaluation will comprise three phases.

3.1 Phase 1

In Phase I, academic and grey literature will be reviewed to identify stakeholders' theories concerning how ACT can be embedded into MS Specialist services and its impacts. In investigating the theoretical basis for work-focused ACT in this setting, we wish to understand the mechanism through which the intervention might be expected to 'work'. The precise search terms and inclusion and exclusion criteria for the literature review will be determined by the project team, in collaboration with subject-specialist librarians at the University of Leeds and Birkbeck University of London. We will conduct an exhaustive literature search of available health, psychology and social science databases that index research relevant to the topics above. The literature review will be used to inform the development of case studies in Phase 2 by reviewing the mechanisms by which READY for MS may work in this setting and the outcomes it may impact on. Specifically, it will inform development of the interview schedule and more broadly to situate the findings and conclusions of this study in the wider literature.

3.2 Phase 2

In Phase 2, a multi-site case study (n=4 in each site) to test and refine the candidate theories will be conducted. The case studies will include interviews with PwMS (pre-intervention/post-intervention/6 months follow up) and ACT facilitation staff (MS Specialist nurses). Participants/staff will be purposively sampled to provide maximum variation and information-rich cases (Patton, 1990; Mason, 2002).

3.3 Phase 3

In Phase III, 2 consensus workshops of 1 hour each will be conducted with 6-8 participants including PwMS and clinical staff to assess the extent to which the results of Phase II are generalisable and to refine the resulting theories to reflect the experience of a broader range of users and implementing health services.

Overall analysis: the analysis from phases 1 & 2 will be synthesised to determine what works for whom in what circumstances.

FOLLOW UP: Patient reported-outcome measures will be completed at baseline, 8 weeks and 6 months. Email/telephone reminders will be sent at each time point.

ANALYSIS: The primary outcome will be analysed using a linear mixed model, including assessments at all available time points (baseline, 8 weeks and 6 months) and include as fixed effects: trial arm, time, arm by time interaction and other important baseline covariates with participant treated as a random effect to account for the repeated measures within subjects.

TIMELINE: MS-PROACTIVE duration - 24 months: Adaptation of the intervention and trial setup - 6 months; Recruitment and randomisation - 6 months; RCT follow up - 6M; data analysis & report writing - 6 months.

All personal and patient identifiable data will be processed in accordance with the European Union General Data Protection Regulation (GDPR) and the UK Data Protection Act 2018.

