5.2 Sampling

5.2.1 Size of sample

This study aims to recruit 88 PwMS who are in paid employment and have medium or high work instability to participate in the randomised controlled pilot trial.

The sample size calculations are based on estimating participation and attrition rates and standard deviation of the primary outcome. If we identify 176 eligible subjects, we will be able to estimate a

participation rate of 50% to within a margin of error of $\pm 7\%$ and an attrition rate of 20% to within $\pm 8\%$

(Hertzog, 2008). Furthermore, an external feasibility study of at least 70 measured subjects will provide robust estimates of the standard deviation of the outcome measure to inform the sample size calculation for the subsequent larger definitive fully powered trial (Teare et al., 2014).

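### The protocol names efficacy as the trial's main purpose, but the 88 participants are justified only for estimating participation, attrition and an SD

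*Protocol*

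**What the plan says.** **Purpose.** The Design paragraph of Section 3 calls the study an external pilot and then states "The main purpose is to assess the efficacy of the new online version of READY for MS". Section 2.1 lists the objective "To assess the efficacy of using web-based ACT versus standard care in a randomised study", and the Study Summary carries the same aim. Three other places point the same way: the second aim in Section 2 is to see whether the programme works, the Plain English Summary says the questionnaires will be analysed for treatment effectiveness, and Section 6.1 describes the main purpose as finding out whether an effect on work instability can be measured. Elsewhere the Plain English Summary gives a different purpose: "This trial aims to adapt and measure the feasibility of using an online version of this course in the NHS". The third objective in Section 2.1 is to supply data for a later definitive trial.

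**Outcomes.** Sections 2.2 and 3 give MS-WIS at 6 months as the primary outcome. The secondary outcomes are other questionnaires. Participation and attrition are not listed in either place. Section 3 says adherence and programme completion will be measured but does not make them outcomes.

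**Sample size.** Section 5.2.1 says "This study aims to recruit 88 PwMS who are in paid employment" and have medium or high work instability, and gives the basis: "The sample size calculations are based on estimating participation and attrition rates and standard deviation of the primary outcome". It counts on at least 70 measured participants for the SD and leaves a fully powered comparison to a subsequent trial.

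**The concern.** The protocol gives the trial two purposes, and its sample size serves only one of them. A reader who takes the main-purpose sentence at face value will judge the trial by its between-arm MS-WIS result, yet nothing in Section 5.2.1 claims that 88 participants can settle that question. The quantities that did set the sample size are absent from the outcome lists, so the results the pilot is best able to deliver have no formal place among them.

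What is at stake is how the result is read. If moderate effects would often be missed, a non-significant difference says little about whether the programme works. The protocol contains no statement that the MS-WIS comparison is preliminary.

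**Working it through.** **Step 1. Reproduce the plan's own figures (Section 5.2.1).** The 95% half-width of a proportion is 1.96 × √(p(1−p)/n).

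- Participation, 50% of 176: 1.96 × √(0.25/176) = 7.4% (stated ±7%).
- Attrition, 20% of 88: 1.96 × √(0.16/88) = 8.4% (stated ±8%).
- Randomised: 176 × 0.5 = 88.
- Measured: 88 × 0.8 = 70.4, which matches the stated minimum of 70.

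The 88 is arithmetically right for its stated basis.

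**Step 2. Inputs for the between-arm comparison.**

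- From the protocol: 1:1 allocation ("RANDOMISATION: 1:1 by patient") and at least 70 measured, so 35 per arm.
- Assumed, because the protocol gives none: two-sided alpha 0.05; true differences of 0.2 to 0.6 SD; correlation ρ between baseline and 6-month MS-WIS of 0 (unadjusted), 0.5 or 0.7. Baseline adjustment multiplies the SD by √(1−ρ²), which is 0.866 at ρ = 0.5 and 0.714 at ρ = 0.7.

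**Step 3. Precision.** The 95% CI half-width in SD units is t(0.975, 68) × √(2/35) × √(1−ρ²).

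- Unadjusted: 1.995 × 0.239 = 0.48.
- ρ = 0.5: 0.477 × 0.866 = 0.41.
- ρ = 0.7: 0.477 × 0.714 = 0.34.

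**Step 4. Power.** Two-sample t-test from the noncentral t distribution with 68 degrees of freedom and noncentrality d × √(35/2) / √(1−ρ²), where d is the true difference in SD units.

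| True difference | Unadjusted | ρ = 0.5 | ρ = 0.7 |
|---|---|---|---|
| 0.2 SD | 13% | 16% | 21% |
| 0.3 SD | 24% | 30% | 41% |
| 0.4 SD | 38% | 48% | 64% |
| 0.5 SD | 54% | 66% | 82% |
| 0.6 SD | 70% | 82% | 93% |
| Difference with 80% power | 0.68 SD | 0.59 SD | 0.49 SD |

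**Step 5. Sensitivity to retention.** Section 6 reports response of 88% at the last of four time points in an earlier questionnaire study at Leeds. Applied here, 0.88 × 88 gives about 77 measured. Power at 0.5 SD is then 58% unadjusted, 71% at ρ = 0.5 and 86% at ρ = 0.7. At 0.3 SD it is 25%, 32% and 44%.

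**The case against.** The strongest reply is that the protocol already limits its claim. It calls itself a pilot throughout, tells participants that it is small, names supply of data for a definitive trial as an objective, and defers full power to that trial. Feasibility is not neglected either: Section 3 gives the methods of recruitment, randomisation and follow-up to the process evaluation, and Section 5.2.1 commits to estimating participation and attrition with stated margins. This stands as evidence of intent. It does not remove a sentence that names efficacy as the main purpose, and it is what makes that sentence inconsistent with the rest. The three process-evaluation phases (literature review, case studies with four participants per site, consensus workshops) are not described as estimating either rate.

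A second reply is that 35 per arm is a floor and that the mixed model uses all available time points, so partial completers contribute. That is fair. Step 5 shows the gain is modest, and Section 3 itself warns of high attrition with online treatment.

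Three stronger readings are tempting but unsupported. A reader might infer that the trial cannot answer the efficacy question at all, or that a non-significant result is the likely outcome. Neither follows: the documents give no expected effect, and at 0.5 SD power ranges from 54% to 82%. A reader might also infer that a null result would be reported as lack of efficacy and stop the definitive trial. No section sets a significance threshold or a rule for proceeding based on MS-WIS, and the SAP, which may address interpretation, is not shown. Nor does the mismatch require MS-WIS to be demoted or a proceed rule added; those are design preferences.

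**Conclusion.** The contradiction holds. Efficacy is stated as the main purpose, while the sample size rests on feasibility quantities that are missing from the outcome lists, and the Plain English Summary names feasibility as the aim. The trial is not designed to assess efficacy reliably: with 35 measured per arm, 80% power needs a true difference of 0.49 to 0.68 SD depending on the baseline correlation, and the confidence interval extends 0.34 to 0.48 SD either side of the estimate. A non-significant MS-WIS result would not show lack of efficacy.

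These sizes depend on the assumed alpha, effect sizes and correlations. The contradiction itself does not. Because the sample size is right for its own basis and no data or patients are affected, this is a should-fix point.

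**What to change.** - In the Study Summary, Section 2.1 and the Design paragraph of Section 3, restate the main purpose as estimating participation, attrition, programme completion and the SD of MS-WIS to inform the definitive trial.
- Bring the matching wording in the Plain English Summary, the aims in Section 2, and Section 6.1 into line.
- Add participation, attrition and programme completion to the outcomes in Section 2.2 and in the repeated list in Section 3.
- Keep MS-WIS as the main clinical outcome. State that it will be reported as a preliminary between-arm estimate with a 95% confidence interval, with no conclusion of efficacy or of no effect.

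The 88 need not change. The cost is a protocol amendment to wording, handled under Section 6.2.2, and a more modest stated claim. No extra participants or data are needed.
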